**Study Title: Prospective randomized clinical trial comparing outcomes of secondary intention wound care methods**

people are enrolled, then enrollment will stop until a patient completes the study, at which point randomized enrollment will resume.

**Study Design / Procedures:**

Randomized Clinical Trial

**Enrollment** At the baseline visit, after the patient has signed consent and been randomized to their specific treatment arm, we will obtain basic demographic information including age, sex and race, as well as pertinent comorbidities that would affect wound healing such as diabetes, venous stasis, immunosuppression and tobacco use (if documented as problems in the patient's chart). Wound defect width, length, and depth will also be measured at baseline, prior to any intervention.

**Intervention Arms:** 1) Aggressive debridement: Aggressive and frequent debridement of fibrin and crust from the wound base down to pinpoint bleeding, both by the patient as part of daily wound care at home, and also by the clinician (either physician or experienced dermatologic surgery nurse) during follow-up visits. Silver nitrate will be used to treat excessive granulation tissue only if the granulation tissue is higher than the level of surrounding skin. Patients will return weekly until healed. Patients will be provided with detailed instructions and guidelines to help determine whether healing has taken place.

2) Minimal debridement: No debridement of fibrin by the patient or the clinician. Exceptions include debridement of dried crust or eschar. Silver nitrate will be used to treat excessive granulation tissue only if the granulation tissue is higher than the level of surrounding skin. Patients will return every two weeks until healed. In between visits at weekly intervals, the patient will be contacted by phone to determine if healing has occurred in between clinic visits. Patients will be provided with detailed instructions and guidelines to help determine whether healing has taken place.

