**Subject Enrollment: / Consent Process / Screening / Randomization:**

Randomization

Block randomization using randomly-permuted block sizes of four and six will be used to ensure balanced enrollment in each arm as the trial progresses. Randomization will also be stratified by anatomic region. The three anatomic regions include: head and neck (5 per arm), trunk and upper extremity (5 per arm), and lower extremity (10 per arm). Randomization sequences will be generated in advance using an available web service and the list will be maintained by a research nurse not involved in patient enrollment. (Sealed Envelope Ltd. 2015. Create a blocked randomization list. [Online] Available from: <https://www.sealedenvelope.com/simple-randomiser/v1/lists> [Accessed 12 Oct 2015].) Treatment allocation assignment for each patient will be kept in sealed envelopes by the research nurse until after the patient is enrolled in the study. As patients are being enrolled, the clinician enrolling the patient will contact this research nurse to obtain the treatment assignment and will not have a priori knowledge of the randomization of the patient. In order to ensure a manageable caseload, only 10 patients will be enrolled in the study at any one time. Once 10

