**Study Title: Prospective randomized clinical trial comparing outcomes of secondary intention wound care methods**

of wound (width, length, and depth); whether the wound is completely healed (completely re-epithelialized); any tumor recurrence (as determined by physician); if excess granulation tissue is present (as determined by being higher than the level of the surrounding skin); if there is infection (as determined by the physician); whether culture was taken; and degree of debridement (none, mild, moderate, or severe).

- At each visit, we will review the treatment method with the patient (i.e. whether aggressive or minimal debridement), reinforce the instructions, and give them another written copy of their wound care methods)
- We will measure time to 50% healing of the wound for all patients.
- *Both intervention arms (aggressive debridement and minimal debridement) are accepted methods of post-operative care for secondary intention wounds. While both methods are practiced at Lahey Clinic, there is no known, published “standard-of-care” in the literature for such wounds. This is because there have been no randomized controlled trials undertaken comparing efficacy of these two methods. That is the purpose of this study.*
- *It is the standard of care to have patients with wounds healing by secondary intention return to clinic for wound checks until the wounds is sufficiently healed; however, the exact interval period is up to the discretion of the provider. In this study, we will be following up weekly with patients receiving frequent debridement and biweekly with patients receiving minimal debridement. All patients will continue to be followed until their wounds are healed.*

Ongoing Care: The patient will return to clinic for evaluation until defect is completely healed, as determined by the principal investigator.

The follow-up intervals are as noted above.

- Patients will be asked to record the date on which their wound healed, and this will be reviewed over the phone or at their next clinic appointment.

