- Once the wound is determined to be completely healed (full re-epithelialization), the patient will be asked to complete the Patient Scar Assessment Questionnaire. The Patient Scar Assessment Questionnaire is a validated questionnaire used standardly in Dermatology for assessing patient-based outcome measures of scarring. It consists of 5 subscales: appearance, symptoms, consciousness, satisfaction with appearance and satisfaction with symptoms. Each subscale consists of a set of items with 4-point categorical responses, scoring 1 to 4 points (with 1 point assigned to the most favorable category and 4 assigned to the least favorable). It has been demonstrated to be a reliable and valid measure of patients' perception of scarring.

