**Statistical Issues**

Sample Size/Power	Time to healing will be the primary outcome measure and will be compared between groups using a two-sided t-test. There is limited literature regarding similar patients to help guide estimates for a power analysis. Based on a review of the literature,  and a brief review of patients previously seen at our clinic, we powered the study to detect a difference in healing time between treatment groups of 14 days, and assumed a standard deviation (SD) of 15 days. To obtain 80% power to detect such a difference, assuming alpha=0.05 and a two-sided t-test, 20 patients per group (40 total) are required.
Anticipated Strengths	We performed a priori power analysis. We are using a randomized study design with validated survey instruments. We plan to use a blinded reviewer of the final cosmetic outcome.
Anticipated Limitations	Given the nature of our study, it will not be possible to conceal treatment arm to patients or providers, though assessment of the final outcome will be by blinded reviewer. If variability in wound healing is greater than anticipated, we may not have statistical power to detect differences between groups; however, the estimates we obtain will help inform future studies. The minimal debridement group will be seen by the clinician every two weeks; while the aggressive debridement group will be seen weekly. It is therefore possible that ascertainment of time to wound healing will differ between groups. However, we hope to avoid this bias checking with the minimal debridement group by phone on weeks where they have no scheduled visit.

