**Statistical Analysis:**

Analytic Plan

Differences in demographic and wound characteristics between groups will be compared to evaluate balance between groups. Differences between treatments arms for the primary (time-to-healing) and continuous secondary outcomes (patient satisfaction with their scar, cosmetic appearance, number of complications) will be analyzed using t-tests for independent groups. If time-to-healing is not distributed normally, or if there are censored observations (e.g., loss to follow-up, or not all patients have healed by the 16-week endpoint), a log-rank test will be used to test for differences in

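### Baseline wound size appears to be measured after the arm is known, which exposes the time-to-50%-healing reference and the wound balance check to observer bias; the primary outcome is not affected

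*Combined protocol and SAP*

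**What the plan says.** The Enrollment paragraph of Study Design / Procedures sets the order of the first visit. Demographics and chart-documented comorbidities are obtained "At the baseline visit, after the patient has signed consent and been randomized to their specific treatment arm". The paragraph then adds: "Wound defect width, length, and depth will also be measured at baseline, prior to any intervention".

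Under Subject Enrollment / Consent Process / Screening / Randomization, the list is held by a research nurse who does not enroll patients, and "the clinician enrolling the patient will contact this research nurse to obtain the treatment assignment". Anticipated Limitations, in Statistical Issues, concedes that "it will not be possible to conceal treatment arm to patients or providers". The only blinded assessor in the document rates photographs of healed wounds.

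Baseline size has two visible uses. The Notes to Study Design / Procedures state: "We will measure time to 50% healing of the wound for all patients". The Analytic Plan states: "Differences in demographic and wound characteristics between groups will be compared to evaluate balance between groups".

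**The concern.** Measuring before any intervention keeps the treatment itself from altering the baseline value. It does not keep knowledge of the arm from influencing how the wound edge is judged or the dimensions rounded. A baseline variable is secure when it is fixed before allocation is known, and the written order does not provide that.

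Two uses are at stake. A shifted baseline size moves the 50% threshold for that patient, so a systematic shift in one arm would look like a difference in early healing. And if the arms differ in recorded wound size, the balance comparison cannot separate chance imbalance from observer bias.

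**Working it through.** **The plan's own figure.** The only calculation in the document is the sample size: a 14-day difference, SD 15 days, two-sided alpha 0.05, 80% power. The exact t-test solution for a standardized difference of 14/15 is 19.03 per group, which rounds up to the stated 20; power at 20 per group is 82.0%. The figure reproduces. It does not depend on when baseline size is measured.

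**Sequence.**
1. The clause placing data collection after randomization belongs grammatically to the sentence on demographics and comorbidities. The wound sentence follows and joins it by saying that size is also measured at baseline. Measurement after randomization is the natural reading, though not stated word for word.
2. Nothing elsewhere places the measurement earlier. The Study Calendar has consent and randomization on Day 1 and mentions no prior measurement.
3. The enrolling clinician knows the arm once the nurse has been contacted, and providers are unblinded throughout. No independent measurer and no measuring method are named. That the measurer knows the arm therefore follows by inference.

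**Where baseline size enters.**

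| Item | Uses baseline size? |
|---|---|
| Primary: time to healing, judged by full re-epithelialization | No |
| Listed secondary outcomes: scar questionnaire, cosmetic rating, number of debridements, failures at week 16, complications | No |
| Planned tests: t-test or log-rank; chi-square or exact | No; no covariate |
| Subgroups by anatomic site | No; site is a randomization stratum, so it is known before assignment |
| Time to 50% healing | Yes, as the natural reference |
| Balance of wound characteristics | Yes |

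**Illustration of size.** None of the following inputs is in the documents: 50% is taken to mean area, full closure is at T = 42 or 56 days, and baseline area is overstated by a fraction e in one arm only. An overstatement of 5% in each of length and width gives 1.05² = 1.1025, about 10% in area; 10% in each gives 1.10² = 1.21, about 20%.

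If the radius shrinks linearly, A(t) = A0(1 − t/T)². The recorded threshold is 0.5·A0(1 + e), reached at t = T[1 − √(0.5(1 + e))]. If area shrinks linearly, t = T[1 − 0.5(1 + e)].

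| e | Linear radius: t/T | Change | Days, T = 42 | Days, T = 56 | Linear area: t/T | Change |
|---|---|---|---|---|---|---|
| 0 | 0.293 | none | 12.3 | 16.4 | 0.500 | none |
| 5% | 0.275 | 6% sooner | 11.6 | 15.4 | 0.475 | 5% sooner |
| 10% | 0.258 | 12% sooner | 10.9 | 14.5 | 0.450 | 10% sooner |
| 20% | 0.225 | 23% sooner | 9.5 | 12.6 | 0.400 | 20% sooner |

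Understatement acts the other way: under linear radius shrinkage, a 10% understatement makes the 50% point about 12% later. Time to complete healing moves by 0 days in every row, because its threshold does not involve A0.

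**The case against.** The strongest reply is that little depends on this. Time to 50% healing appears once, is not under Outcomes Measures, has no analysis in the Analytic Plan, and is not defined as area, length, depth or volume. What remains is a descriptive balance check. This stands, and it limits the point to a minor one.

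The illustration needs an error that is systematic and differs between arms. Error common to both arms would not produce the between-arm shift shown. The documents give no error rate. The hypothesis is directional, but that does not establish which arm's wounds would be overstated. This also stands.

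The same endpoint has a larger problem. Follow-up sizes are also taken open-label, at visits every 7 days in one arm and every 14 in the other, and the intervening phone calls ask only whether the wound has healed. If crossing times fall evenly between visits, mean detection delay is 7/2 = 3.5 days against 14/2 = 7 days. That 3.5-day gap exceeds the 16.4 − 14.5 = 1.9-day shift illustrated for a 10% error at T = 56. Reordering the baseline step does not cure it. That is no reason to leave a free correction unmade.

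Three stronger readings are tempting and not supported:
- A reader might infer that the primary comparison is biased. It is not by this route, since full re-epithelialization makes no reference to starting size.
- A reader might infer that an adjusted analysis would inherit the bias. The plan has none: the primary and continuous secondary outcomes "will be analyzed using t-tests for independent groups", with a log-rank test for healing time if the data are non-normal or censored.
- A reader might infer that patients who withdraw on learning their arm would leave no baseline record. Comorbidities come from the chart, so mainly wound size would be lost, and nothing suggests that such withdrawals are expected.

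**Conclusion.** The point holds as a minor design weakness. As written, the protocol places baseline data collection after randomization and protects wound measurement only from the treatment, not from knowledge of the arm. That the wound is measured after allocation is the natural reading of the text, and that the measurer knows the arm is a reasonable inference; neither is stated outright.

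The exposure is confined to the reference for time to 50% healing and the wound-characteristic balance check. The primary outcome, the listed secondary outcomes and the sample size are unaffected. The size of any bias cannot be estimated from the documents. The figure of about 12% sooner for a 10% overstatement of area in one arm assumes linear radius shrinkage (10% under linear area shrinkage) and shows sensitivity only; it does not predict what would happen.

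**What to change.** Reorder the Enrollment paragraph: consent first; then demographics, comorbidities and wound width, length and depth entered on the data collection form; only then does the clinician contact the research nurse for the assignment. Add that no baseline value may be changed on account of the allocation once it is known. If the clinic already works in this order, one sentence saying so settles the point.

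The cost is a short change of text. Visit, staff, measurements and the 20 patients per arm stay the same. The change cannot be applied retrospectively to patients already enrolled. It also leaves open-label follow-up measurement and the weekly versus two-weekly visits as they are, so time to 50% healing would still need cautious interpretation.

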**Study Title: Prospective randomized clinical trial comparing outcomes of secondary intention wound care methods**

**Participant Selection / Eligibility:**

Subjects

- 1) Dermatology patients at Lahey Clinic
  - 2) who have undergone Mohs surgery or excision
  - 3) who are older than 18 years
  - 4) who are able to give consent
  - 5) who had postoperative defects allowed to heal by secondary intention on the a) head and neck, b) trunk and upper extremities, c) lower extremities
  - 6) who are willing and able to return to clinic in Peabody for all wound care visits

Exclusion Criteria

- 1) Unable to consent (due to language barrier, mental status)
- 2) Unable to perform daily wound care
- 3) Unwilling or unable to return for follow-up
- 4) Have baseline venous stasis or pitting edema of the affected limb
- 5) Wear compression stockings or require use of a compressive bandage (such as an Unna Boot) at baseline.

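### The primary comparison uses neither the recorded baseline wound size nor the stratification region, so it is valid but gives up precision that prespecified adjustment could recover

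*Combined protocol and SAP*

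**What the plan says.** - **Eligibility** (Participant Selection / Eligibility) takes patients "who had postoperative defects allowed to heal by secondary intention on the a) head and neck, b) trunk and upper extremities, c) lower extremities". Neither the inclusion nor the exclusion list limits width, length or depth.
- **Randomization** (Subject Enrollment section) uses permuted blocks stratified by three anatomic regions, planned at 5, 5 and 10 patients per arm. Wound size is not a stratification factor.
- **Baseline data** (Study Design / Procedures, Enrollment): "Wound defect width, length, and depth will also be measured at baseline, prior to any intervention". The same paragraph places the baseline data collection after consent and randomization.
- **Sample size** (Statistical Issues): "Time to healing will be the primary outcome measure and will be compared between groups using a two-sided t-test". The study is powered for a "difference in healing time between treatment groups of 14 days", and the authors "assumed a standard deviation (SD) of 15 days", giving 20 per group.
- **Analysis** (Statistical Analysis): independent-groups t-tests, replaced by a log-rank test if healing times are non-normal or any are censored. No covariate or stratum is named for either. Wound characteristics appear once: "Differences in demographic and wound characteristics between groups will be compared to evaluate balance between groups". No action is attached to that comparison. Anatomic site enters only through exploratory subgroups.

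**The concern.** The outcome is time to complete re-epithelialization, so the amount of wound to be closed is a plausible predictor of it, and eligibility lets that amount vary freely. If size does predict healing time, its spread stays in the error term of an unadjusted test, and any chance difference in size between two arms of 20 becomes part of the estimated treatment difference. Inspecting balance does not correct this. Because no rule says what follows from an observed imbalance, any later adjustment would be chosen after seeing the data, in a trial where patients and providers know the arm. Region raises a similar issue: it is built into the allocation but left out of the primary test. At stake is how much a 40-patient trial can learn from data it already plans to collect.

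**Working it through.** **Inputs from the documents (Statistical Issues).** Difference 14 days; SD 15 days; 20 per arm; "To obtain 80% power to detect such a difference", "assuming alpha=0.05 and a two-sided t-test".

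**Assumption.** The documents give no correlation r between baseline size and healing time. I use r = 0.3, 0.5 and 0.7, with 15 days as the total SD.

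**1. The plan's own figure.** The noncentral-t calculation gives power 79.9% at 19 per arm and 82.0% at 20. The stated 20 per group reproduces.

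**2. Precision of the planned test.** SE = 15 × √(2/20) = 4.74 days. With 38 df, t = 2.024, so the 95% CI half-width is 2.024 × 4.74 = 9.6 days.

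**3. Effect of adjusting for size.** Residual SD = 15 × √(1 − r²), with 37 df (t = 2.026).

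| Assumed r | Residual SD (days) | SE (days) | Half-width (days) | Power for 14 days |
|---|---|---|---|---|
| unadjusted | 15.0 | 4.74 | 9.6 | 82.0% |
| 0.3 | 14.3 | 4.53 | 9.2 | 85.4% |
| 0.5 | 13.0 | 4.11 | 8.3 | 91.3% |
| 0.7 | 10.7 | 3.39 | 6.9 | 98.0% |

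A 10,000-run simulation of the adjusted analysis gave slightly lower power: 84.4%, 90.8% and 97.5%. Adding region costs two more df (35 left, t = 2.030), which changes each half-width by about 0.02 days before any gain from region itself.

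**4. Chance imbalance.** Ignoring the region strata, the standardized size difference between arms has SE √(2/20) = 0.32, so a gap above 0.5 SD has probability about 11%. A one-SE gap moves the unadjusted estimate by r × 15 × 0.316 = 1.4, 2.4 or 3.3 days.

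**5. Steps 3 and 4 describe the same variance.** At r = 0.5 the imbalance component is 2.37 days and the residual component 4.11 days, and 2.37² + 4.11² = 5.6 + 16.9 = 22.5 = 4.74². The 9.6-day half-width therefore already allows for chance size imbalance, and the two effects must not be added.

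**6. Validity.** In simulation the unadjusted t-test rejects a true null about 5% of the time overall. Among trials with a size gap above 0.5 SD the rate is about 14% at r² = 0.25 and 22% at r² = 0.50.

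**7. If the SD is larger than planned.** At an assumed total SD of 20, unadjusted power is 57.8%. Adjustment gives 62.3%, 70.2% or 86.2% for r² = 0.10, 0.25 or 0.50.

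**The case against.** The strongest reply is that nothing here is broken. Randomization keeps the unadjusted test valid, its interval already allows for chance imbalance, and it has 82% power against a target of 80%. That stands. A reader might infer from the open eligibility and region-only stratification that the trial is biased, underpowered or wrongly randomized. The documents do not support this: the sample size reproduces, type I error holds overall, and an analysis-only change needs no new entry limit or stratum.

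Second, the gain rests on an assumed correlation. Nothing in the documents calls wound size a major prognostic factor. At r = 0.3 the simulated gain is only 2 to 3 points of power. This also stands.

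Third, stratifying by region may already balance part of the size variation, so it would be too strong to say that no part of the plan controls for size. The 11% figure and the gains in the table are then somewhat too large. But region is absent from the primary test, and size can still vary within each region.

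Fourth, every figure above is for a linear model without censoring, whereas a single unhealed wound at week 16 triggers the log-rank fallback. The gain there is not quantified here, and a Cox model adds assumptions that the log-rank test does not need.

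Fifth, area leaves depth out, and the log scale is an analyst's choice that the documents do not dictate. Both are fair. One size term is a compromise suited to 40 patients.

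What the reply does not answer is why a pre-treatment measurement already taken on every patient should be left out of the primary comparison.

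**Conclusion.** The point holds as an opportunity to improve precision. The primary analysis ignores recorded baseline wound size and the stratification factor. The cost is forgone precision and exposure to chance imbalance, counted once. If the size-healing correlation is 0.3, 0.5 or 0.7 within an SD of 15 days, adjustment would take the half-width from 9.6 days to about 9.2, 8.3 or 6.9 and power from 82% to about 85%, 91% or 98%. These figures assume a linear relation, no censoring, and no overlap between region and size; overlap would reduce the gain. If size is unrelated to healing time, a simulation put the loss at about one point of power (81.0% against 82.1%). The planned balance check does not close the gap, because it leads to no action.

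**What to change.** In Statistical Analysis, prespecify:

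- **Primary comparison:** a linear model of healing time on arm, log baseline wound area (width × length) and anatomic region.
- **Fallback for censoring or non-normality:** a Cox model with arm and log area, stratified by region.
- **Supportive analysis:** the t-test or log-rank test as now planned, unadjusted.

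In Study Design / Procedures, state that the wound is measured before the allocation is disclosed. Baseline collection is now described after randomization, and Statistical Issues acknowledges that the arm cannot be concealed from patients or providers, so a covariate in the primary model should be fixed before anyone knows the arm.

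**Cost:** three degrees of freedom in the linear model (one for area, two for region), a set order for one baseline step, and, in the fallback, a proportional-hazards assumption and a hazard ratio that is conditional on the covariate. No new data, visits or patients are needed. Eligibility and randomization stay as they are.
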